3.3 Exclusion Criteria

Any subject meeting any of the exclusion criteria will be excluded from study participation.

1. With active osteomyelitis

3.5 Subject Replacement

[Redacted text]

3.6 Concomitant Medications

[Redacted text]

[Redacted text]

[Redacted text]

[Redacted text]

[Redacted text]

[Redacted text]

4. STUDY DESIGN

This study is designed as a randomized, double-blind, vehicle-controlled, multiple center and parallel trial to evaluate the efficacy and safety of CSTC1 in patients with diabetic foot ulcer.

The potential subjects with diabetic foot ulcer at Screening visit will be arranged to enter an initial phase for 2 weeks in which subjects receive only standard of care, unless subject has receive any other regular therapy for at least 2 weeks. Subjects whose study ulcer size decreases by at least 30% during this initial standard-of-care phase or previous regular therapy period will be excluded from the study at investigator's discretion. The remaining eligible subjects will be randomly assigned to receive either one of topical application of CSTC1 dose or CSTC1 matched vehicle, 2 times daily.

The treatment duration for each subject is 12 weeks or up to confirmed complete ulcer closure, whichever comes first. That is, subjects will receive treatment for at most 12 weeks, which consists of 8 visits located at weeks 1, 2, 3, 4, 6, 8, 10, and 12. Subjects confirmed complete ulcer closure during treatment period will be arranged for a 12 week post-treatment follow-up. Subjects failed to achieve complete ulcer closure at week-12 visit will be arranged for 4 weeks of safety follow-up. Subjects happening to attain complete ulcer closure at week-12 visit will not receive further treatment but needs to be confirmed at week-14 visit. If confirmation of complete ulcer closure is reached at week-14 visit, the subject will continue the post-treatment follow-up visit until week-24 visit. Otherwise, the subject will be arranged for safety follow-up until week-16 visit.

After the treatment period, the post-treatment follow-up period for subjects confirmed complete ulcer closure will consist of 4 visits at weeks 2, 4, 8, 12 after confirmation of complete ulcer closure. The safety follow-up period for subjects failed to achieve complete ulcer closure at week-12 visit will consist of 2 visits at weeks 14 and 16.

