Subjects Exclusion Criteria	
Any subject meeting any of the exclusion criteria will be excluded from study participation.
 
 1. With active osteomyelitis 2. With target ulcer size decreased by at least 30% after at least 2 weeks of standard-of-care-only period or any other recorded regular therapy before Randomization visit 3. With poor nutritional status (albumin < 2g/dl), poor diabetic control (HbA1c > 12%), anemia (hemoglobin < 8 g/dL), a leukocyte counts < 2,000/mm³, abnormal liver function (AST, ALT>3 x upper limit of normal range) 4. Requiring treatment with systemic corticosteroids, immunosuppressive or chemotherapeutic agents within 28 days prior to Screening visit 5. Presence of necrosis, purulence or sinus tracts that cannot be removed by debridement 6. Receiving revascularization surgery or endovascular therapy performed <8 weeks before entry in the study 7. With known or suspected hypersensitivity to any ingredients of study product and vehicle 8. With coronary heart disease with myocardial infarction, coronary artery bypass graft (CABG), or percutaneous transluminal coronary angioplasty (PTCA) within 3 months prior to study 9. Pregnant or lactating or premenopausal with childbearing potential but not taking reliable contraceptive method(s) during the study period 10. Enrollment in any investigational drug trial within 4 weeks before entering this study 11. With any uncontrolled illness judged by the investigator that entering the trial may be detrimental to the subject
Primary Endpoint	
Efficacy:
 
The incidence of complete ulcer closure during up to 12 weeks of treatment period
 
Complete ulcer closure is defined as 100% skin re-epithelialization without drainage or dressing requirements confirmed at two consecutive study visits 2 weeks apart. Subjects with complete ulcer closure at week-12 visit and confirmed at week-14 visit will be considered as success.

Secondary Endpoints Efficacy:

1. The ulcer closure time
Defined as the time to complete ulcer closure
2. The complete ulcer closure rate
The proportion of subjects with complete ulcer closure at each post-treatment visit
3. Percentage change in ulcer size for each post-treatment visit
Calculated as (Ulcer size at post treatment visit - Ulcer size at baseline)/(Ulcer size at baseline)

Safety:

1. Adverse event incidence
2. Change in physical examination results

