Additionally, descriptive statistics will be provided for all of the endpoints. Frequency table will be provided for categorical data, while mean, standard deviation, maximum, minimum, median, inter-quartile range (IQR), and 95% two-sided confidence interval will be calculated for continuous measurements. In addition, endpoints of time to event will be presented by using the life table and Kaplan-Meier plot. The Kaplan-Meier estimates will also be provided for these time-to-event endpoints.

All treatment group comparisons will be conducted with significance level of 0.05.

SCHEDULE OF ASSESSMENTS

	Screening ¹	Initial ² Phase	Randomization ³ (Baseline)	Dosing/Observation								Follow-up			
	1	2	3	4	5	6	7	8	9	10	11 ¹¹	12	13	14	15
Week relative to Baseline visit	-3~-2	-2~0	0	1	2	3	4	6	8	10	12	14	16	20	24
Visit Window (days)	NA	±4	NA	±4	±4	±4	±4	±4	±4	±4	±4	±4	±4	±4	±4
Informed consent signed and given	X														
Screening number assignment	X														
Randomization			X												
Demographic data & medical history	X														
Inclusion and exclusion criteria	X		X												
Pregnancy test for applicable subjects	X										X				
Ulcer Evaluation ⁴	X		X	X	X	X	X	X	X	X	X	X	X	X	X
Vital signs	X		X	X	X	X	X	X	X	X	X	X	X	X	X
Physical examinations	X		X	X	X	X	X	X	X	X	X	X	X	X	X
Ankle Brachial Index ⁵	X														
Laboratory test: hemoglobin, hematocrit, RBC, platelet, WBC with differential counts, HbA1c, fasting glucose, AST, ALT, creatinine and BUN, albumin	X ⁶		X ⁷								X ⁸				
Record concomitant medication(s)	X	X	X	X	X	X	X	X	X	X	X	X	X	X	X
Standard of Care		X	X	X	X	X	X	X	X	X	X				
Record adverse events (AE) ⁹	X	X	X	X	X	X	X	X	X	X	X	X	X	X	X
Dispense trial medication			X	X	X	X	X	X	X	X					
Returned medication count				X	X	X	X	X	X	X	X				
Diary Dispensing			X												
Diary Return				X	X	X	X	X	X	X	X				
Complete exit form													X		X
Dismiss subject ¹⁰													X		X

Footnote:

- 1: Could be on the same day as the first day of Initial Phase or randomization visit if subject's Initial Phase can be waived
- 2: Can be waived if subject's diabetic foot ulcer(s) has been treated for at least 2 weeks, and is still eligible to enter this study
- 3: Could be on the same day as the last day of Initial Phase
- 4,10: Subjects with confirmed complete ulcer closure up will be arranged for ulcer evaluation for follow-up period; Subjects not with complete ulcer closure will take 4 weeks of safety evaluation

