3. STUDY POPULATION

3.1 Subjects Enrollment

The sample size is determined to be 80 versus 20 subjects (4:1 ratio) for Treatment versus Control groups, 100 subjects in total. To ensure the completion of 100 evaluable (= per-protocol) subjects, around 125 subjects will be recruited. All of the subjects will be recruited in Taiwan. Any subject fulfills all of the recruitment criteria will be screening and/or randomized into the study.

Re-screening for patient's eligibility will be allowed if the patient is willing to participate in the study and one of the following conditions meets:

1. If a patient consents to participate and meets the eligibility criteria but a delay occurs in starting to participate in due to certain change in situation such that some measurement relevant to eligibility became invalid owing to the delay
2. If the cause of screen failure has now resolved or adequately treated such that patient's medications have now stabilized

In these situations, if randomization has not occurred;

1. A new CRF will be used
2. A new Screening number will be assigned to the person
3. The person will be marked as having been re-screened on both the CRF and the site master list
4. The patient needs to sign a new ICF as part of the screening procedure.

It is not appropriate to re-screen a patient if he/she has previously failed to meet the eligibility criteria and no further changes or treatments have been able to indicate that the patient may be suitable.

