4.1 Treatment Assignment

Eligible subjects will be assigned randomization number in sequential order and each of the randomization will determine the allocation of one of the two treatment groups in 4:1 ratio as shown below:

1. CSTC1 two times daily
2. CSTC1 matched vehicle, two times daily

Treatments should be continued for a total of 12 weeks or until confirmation of complete ulcer closure, whichever comes first. After treatment period, additional 12 weeks of follow-up period is arranged for subjects confirmed complete ulcer closure to help distinguish actual ulcer healing from transient ulcer coverage, determine if the investigational product affects the strength of ulcer closure relative to standard care, and monitor for adverse effects on surrounding tissue

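### Section 4 leaves exclusion of ulcers that shrank by at least 30% before randomization to the investigator, while exclusion criterion 2 makes it mandatory

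*Combined protocol and SAP*

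**What the plan says.** The rule on early shrinkage appears twice, with different force.

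- **Protocol Summary, Subjects Exclusion Criteria, item 2.** A subject is excluded if this applies: "With target ulcer size decreased by at least 30% after at least 2 weeks of standard-of-care-only period", or the same decrease on "any other recorded regular therapy before Randomization visit". The lead-in, repeated in Section 3.3, is "Any subject meeting any of the exclusion criteria will be excluded from study participation". Nothing in either text leaves room for judgement.
- **Section 4, Study Design.** Subjects whose study ulcer shrinks by the same 30% or more "during this initial standard-of-care phase or previous regular therapy period will be excluded from the study at investigator's discretion".

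Other text relies on the criteria list:

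- The Schedule of Assessments has a row for "Inclusion and exclusion criteria", marked at Screening and at Randomization, and Section 7.3 has eligibility confirmed again at the Randomization visit.
- Section 3.1 states "Any subject fulfills all of the recruitment criteria will be screening and/or randomized into the study".
- Section 4.1 states "Eligible subjects will be assigned randomization number in sequential order".

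Section 10.2.1 defines ITT as randomized subjects with at least one dose and bases the efficacy conclusion on it. Its per-protocol (PP) definition requires every inclusion and exclusion criterion to be met. Section 3.1 ties recruitment to PP: "To ensure the completion of 100 evaluable (= per-protocol) subjects, around 125 subjects will be recruited".

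**The concern.** Both rules are triggered by the same event over the same pre-randomization period, but one is automatic and the other optional. A site that always excludes these subjects complies with every passage. A site that follows Section 4 literally may randomize a subject whom criterion 2 excludes, and no visible text says which passage prevails.

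Three things are at stake:

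- **Divergence of ITT and PP.** A subject admitted this way and dosed counts in the decisive analysis but not in the PP analysis.
- **Fewer evaluable subjects.** The recruitment margin is set to deliver a PP count, and conduct that Section 4 permits would erode it. Only 20 vehicle subjects are planned.
- **Sensitivity.** If ulcers already closing on standard care tend to close in either arm, including them dilutes the treatment difference. In a multicentre trial, the practice could also differ by site.

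**Working it through.** **1. The passages side by side**

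| | Criterion 2 (Protocol Summary) | Section 4 |
|---|---|---|
| Trigger | Target ulcer smaller by at least 30% | Study ulcer smaller by at least 30% |
| Period | At least 2 weeks of standard care only, or other recorded regular therapy, before randomization | Initial standard-of-care phase (2 weeks), or previous regular therapy |
| Force | Mandatory through the lead-in | At the investigator's discretion |

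In Section 4 the decrease is taken as given and the discretion qualifies the exclusion itself. The next sentence randomizes the remaining eligible subjects. That does not settle the matter, because who remains depends on the discretion just granted.

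**2. The plan's own figures**

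The 4:1 split gives 100 × 4/5 = 80 and 100 × 1/5 = 20, as stated. The target of 125 equals 100 / (1 − 0.20), so the implied PP loss is 20% and the reserve is 125 − 100 = 25. The 20% is inferred; the sample-size section (10.1) is redacted.

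**3. Effect on the PP reserve**

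Recruited is read as randomized and dosed. Let f be the share admitted against criterion 2. The documents do not give f, so 2%, 5% and 10% are assumed.

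- Subjects failing PP for this reason: v = 125 × f
- Part of the reserve used: v / 25
- Loss from all other causes that still leaves 100: (25 − v) / (125 − v)
- PP size if other losses are 20%: (125 − v) × 0.8, one fifth of it on vehicle

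| f | v | Reserve used | Tolerable other loss | PP size | Vehicle |
|---|---|---|---|---|---|
| 0 | 0 | 0% | 20.0% | 100 | 20 |
| 2% | 2.5 | 10% | 18.4% | 98 | 19.6 |
| 5% | 6.25 | 25% | 15.8% | 95 | 19 |
| 10% | 12.5 | 50% | 11.1% | 90 | 18 |

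**4. Effect on ITT power (illustration only)**

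Planned closure rates are redacted, so all rates here are assumptions. Power is by exact enumeration of both binomials for the single-stratum CMH test, two-sided 0.05, at 80:20 and 100:25. The share f is the same in both arms:

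p₁ = (1 − f)·b₁ + f·h₁ and p₀ = (1 − f)·b₀ + f·h₀

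The base rates (b₁, b₀) are 50% vs 20%, 60% vs 30% and 70% vs 40%. The rates in admitted subjects (h₁, h₀) are 80% vs 80%, 90% vs 70% and 80% vs 50%.

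With base 60% vs 30% and admitted subjects closing at 80% in both arms:

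| f | Power at 80:20 | Power at 100:25 |
|---|---|---|
| 0 | 69.3% | 78.8% |
| 2% | 67.4% | 77.1% |
| 5% | 64.6% | 74.4% |
| 10% | 59.8% | 69.6% |

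Loss in percentage points, across all base rates and both sizes:

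| Admitted subjects | f = 2% | f = 5% | f = 10% |
|---|---|---|---|
| 80% vs 80% | 1.5 to 2.3 | 4.0 to 5.6 | 8.2 to 11.3 |
| Other two cases, largest loss | 1.0 | 2.5 | 4.8 |
| All combinations | −0.1 to 2.3 | −0.2 to 5.6 | −0.4 to 11.3 |

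With base 60% vs 30% and admitted subjects at 80% vs 50%, there is essentially no loss.

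**5. Type I error**

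With both arms at (1 − f) × 0.3 + f × 0.8, the exact type I error is 4.84% to 4.97%. The admission decision comes before blinded randomization, so no inflation is expected and none appears.

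**The case against.** The strongest reply is that the criteria list governs and Section 4 is only an overview. The schedule and Section 7.3 check eligibility at randomization, and Section 4.1 gives numbers only to eligible subjects. Harm then needs a site to let one phrase override the list. This makes the mandatory reading more likely, but no visible text ranks the sections, and Section 4 is where the initial phase and its 30% check are described.

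A second reply is that discretion may mean judging whether a 30% decrease occurred, especially over therapy given before study measurements began. That is possible, but the sentence attaches the discretion to the exclusion. If the other meaning was intended, the wording still needs repair.

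Third, the public copy of Section 3.3 breaks off after item 1, so criterion 2 can be read only in the Protocol Summary, and the full Section 3.3 might carry a qualifier. This limit is real. The conflict between the Protocol Summary and Section 4 remains either way, but the sponsor should check the full Section 3.3 before choosing the repair.

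Finally, the shares in the calculation have no source in the documents, and the largest power losses come from one case: no drug effect at all in the admitted subjects. That stands, so the power figures should carry little weight in rating the point. It also stands that ITT decides efficacy, so a smaller PP set does not change the decision rule, and that the redacted Section 3.5 on replacement might offset the loss.

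**Conclusion.** The contradiction holds, and it rests on the wording alone; no assumed figure is needed for it. Criterion 2 under its lead-in makes exclusion mandatory, and Section 4 makes exclusion for the same event optional. It should be fixed, but it does not threaten the validity of the primary test: there is no bias toward either arm and no inflation of type I error.

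The consequence that follows from the plan's own definitions is that each subject admitted under Section 4 and dosed counts in ITT, fails PP and uses one of about 25 reserve places. The total depends on a frequency the documents do not give. The power loss could be nil, and its upper end depends on assumed closure rates.

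**What to change.** Reconcile the two passages. The simplest way is to delete the three words in Section 4 that leave the exclusion to the investigator. Section 4 then agrees with criterion 2, its lead-in, the eligibility checks and the PP definition. Confirm at the same time that item 2 in the full Section 3.3 reads as in the Protocol Summary. If discretion is really intended, criterion 2 and the PP definition would have to be changed to match instead.

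The deletion adds no procedure, visit or data item. Its only cost is that sites lose the option to admit such subjects.

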4.1 Treatment Assignment

Eligible subjects will be assigned randomization number in sequential order and each of the randomization will determine the allocation of one of the two treatment groups in 4:1 ratio as shown below:

1. CSTC1 two times daily
2. CSTC1 matched vehicle, two times daily

Treatments should be continued for a total of 12 weeks or until confirmation of complete ulcer closure, whichever comes first. After treatment period, additional 12 weeks of follow-up period is arranged for subjects confirmed complete ulcer closure to help distinguish actual ulcer healing from transient ulcer coverage, determine if the investigational product affects the strength of ulcer closure relative to standard care, and monitor for adverse effects on surrounding tissue

4.2 Randomization and Blinding

Permuted block randomization method will be applied to generate randomization codes. Each randomization number will be assigned to individual subject according to the time-sequence for screened subject becoming eligible.

Both CSTC1 and its matched vehicle will be prepared to be identical in all aspects to achieve the double-blind purposes. All subjects will take proper amount of CSTC1 or CSTC1 matched vehicle per application to ulcer area.

5. TRIAL MATERIALS

5.1 Trial Product (s)

Topical formulation of CSTC1 is a vapor fraction from seeds of Glycine max (L.) Merr. and composition thereof. The marker ingredients (impurity) of CSTC1 are Raffinose pentahydrate, Stachyose hydrate, Daidzin, and Genistin. The comparator used in this study is CSTC1 matched vehicle. Both investigational products will be applied daily twice a day.

Soybean was extracted using two methods, vapor fraction (C1) and ethanol extraction followed by concentration and drying (A1). 0.3% of A1, shown to reach the most active in wound healing in animal model when combined with the water extracted composition to form the drug substance. The final drug product, CSTC1, contains 0.3% of A1 and 85.95% water extracted composition in a cream base with a total of 30g per tube shown as below:

Code Name	CSTC1
Component	2148.75g C1 and 7.5g A1, cream base 343.75 g
Amount per tube	30g/tube

Cream base, Stearic acid, Stearyl alcohol, Tween 80, Borneol, Potassium hydroxide, Benzyl alcohol

The placebo was made with a cream base and coloring agents with the ingredients and amount as follows:

The active and vehicle cream is manufactured and packed with 30 g in weight in a LDPE tube by Charsire Biotechnology Co., Ltd.

5.2 Storage and Drug Accountability

Adequate supplies of either CSTC1 or CSTC1 matched vehicle will be packaged for one visit dispense. The total number of tubes of investigational product planned for each subject will be 100 and each subject is expected to use at most 1 tube per day. Each subject will be dispensed for up to 8 visits at visits 3 to 10. At each visit of visits 3 to 9, investigational product should be supplied to the subject for use based on the number of tubes of unused investigational product the subject possesses and to the extent of date that the subject may return with remaining eligible for next visit. Therefore, the number of tubes supplied at each visit will be calculated as (date of subject expected to return for next visit – date of current visit + 4 days of time window - number of tubes the subject possesses).

The trial medication for both treatment groups will be packaged in an identical way. Drug accountability will be recorded for the weight of test drug given to the subjects and returned to site by the subjects. Subject will be dispensed diary cards to record the times in each day they apply the study medications to the treated area.

All the products should be stored at room temperature (under 30° C) and be managed by the hospital pharmacies.

5.3 Dose Regimen

[Redacted content]

[Redacted]

5.4 Treatment Compliance

[Redacted]

[Redacted]

[Redacted]

[Redacted]

[Redacted]

- Biochemistry: AST, ALT, fasting glucose, HbA1c, serum creatinine, blood urea nitrogen (BUN), albumin

Laboratory examination will be conducted at Screening visit, Randomization (baseline) visit, and week 12 visit. Albumin will only be test at Screening and Randomization visits for judging subject eligibility. Laboratory test results within 14 days before Screening visit and 28 days before Randomization visit are acceptable; HbA1c test result within 28 days can be accepted.

6.4 Standard-of-Care Procedures

[REDACTED]

[REDACTED]

[REDACTED]

[REDACTED]

[REDACTED]

[REDACTED]

[REDACTED]

[REDACTED]

[REDACTED]

7. STUDY SCHEDULE

This study is designed as a randomized, double-blind, parallel, vehicle-controlled trial. The potential subjects with diabetic foot ulcer may be arranged to enter an initial phase for 2 weeks in which subjects receive only standard of care before randomization. The subjects confirmed eligible at the randomization visit will be randomly assigned to receive either one of CSTC1 or its matched vehicle treatment, two times daily. The subjects in either treatment group will be given 12 weeks of treatment and arranged a 4 week safety follow-up (if not achieving complete ulcer closure at week 12 visit) or be given up to confirmed complete ulcer closure and arranged 12-week post-treatment follow-up (if achieving confirmed complete ulcer closure before or at week-12 visit).

The schedule of assessment is tabulated in front of the protocol main text. The assessments or procedures to be performed at each study visit are listed below. The results of protocol specific assessments and procedures will be recorded in the source documents for all study subjects and on the appropriate page of the CRF.

7.1 Screening visit

(-3 to -2 weeks relative to Randomization (baseline) visit or within 1week randomization visit if initial phase is not required)

1. Explain the nature of the study and have subject to read and sign an Informed Consent Form
2. Assign subject screening number
3. Obtain Demographic, including:
 - Gender
 - Date of Birth
 - Height
 - Weight
4. Screen subject for inclusion/exclusion criteria
5. Medical history, including:
 - History of diabetic mellitus
 - Date of onset of diabetic mellitus
 - Date of onset of first and current episode of diabetic ulcer foot
 - Therapy for current episode of diabetic ulcer foot
 - General medical history: All medical histories within one year before screening visit are to be recorded, using the body system categories outlined below. For each history, the specific medical terminology for the disease/disorder/condition, the date of diagnosis, and the history status (resolved or ongoing) will be documented.
6. Perform pregnancy test for female with childbearing potential (Note: not with childbearing potential means post-menopausal (defined as at least one year without any menstruation) or documented status of post hysterectomy)
7. ABI measurement
8. Vital signs
9. Perform physical examinations

10. Obtain blood samples for hematologic and biochemical tests (Test results within 14 days before screening visit are acceptable; HbA1c test results can be within 28 days.):
11. Ulcer evaluation
12. Record concomitant medication(s)
13. Record adverse event(s)

